10.2.1 AE summaries

An overall summary of TEAEs will provide the number and percentage of study participants with at least one: TEAE, serious TEAE, TEAE requiring dose change, drug-related TEAE, severe TEAE, TEAE leading to permanent discontinuation of study drug, AE leading to death (based on the All Participants Screened Set), and TEAE leading to death. This will be produced for the Overall Period and the Evaluation Period. Additionally, this summary will be presented by modal dose category for the Evaluation Period and for each 3-month period in the Evaluation Period.

Treatment-emergent AEs requiring a dose change will be identified from the AE eCRF where “Action Taken with Study Medication” is “Dose reduced” or “Dose increased”.

All AEs will be summarized overall and by MedDRA primary system organ class (SOC) and MedDRA preferred term (PT). The number and percentage of study participants experiencing each event at least once will be summarized. All summaries will be sorted alphabetically by SOC and by incidence of AEs within PTs, starting with the highest incidence overall. Only the first occurrence of a TEAE of a particular PT will be included in incidence calculations, but all occurrences of TEAEs of the same PT will be included in counts of TEAEs. All summaries will be produced for the Overall Period, Evaluation Period and for each 3-month period in the Evaluation Period except for the incidence of TEAEs leading to permanent discontinuation of study drug which will not be produced for the Overall Period.

The following summaries will be provided:

- Incidence of TEAEs
- Incidence of TEAEs leading to permanent discontinuation of study drug
- Incidence of serious TEAEs
- Incidence of TEAEs by relationship
 - Relationship is related/not related to study drug and is decided by the study investigator.
- Incidence of TEAEs by maximum relationship.
 - Related to study drug is considered more significant than not related to study drug ie, if a study participant has experienced the same TEAE on more than one occasion, where on at least one of the occasions it was considered to be related to the study drug, the maximum relationship is related.
- Incidence of TEAEs not exclusively related to COVID-19 vaccination
 - These will be identified as TEAEs where “Is the Event Related to a COVID-19 Vaccination” is answered “No” on the AE eCRF
- Incidence of TEAEs by maximum intensity
 - Each study participant will be counted at most once per primary SOC or PT according to the maximum intensity of all AEs within that SOC or PT.
- Incidence of non-serious TEAEs above reporting threshold of 5% of participants
- Incidence of non-serious TEAEs not exclusively related to COVID-19 vaccination above reporting threshold of 5% of participants
- Incidence of non-serious TEAEs above reporting threshold of 5% of participants by relationship to study drug
- Incidence of TEAEs of interest
- Incidence of TEAEs of special interest
- Incidence of serious TEAEs by relationship to study treatment
- Incidence of fatal TEAEs by relationship to study treatment

For the PLS the overall summary of TEAEs will be repeated on a subset of TEAEs considered related to study drug per investigator assessment. This will provide the number and percentage of study participants with at least one: drug-related TEAE, serious drug-related TEAE, severe drug-related TEAE, drug-related TEAE leading to permanent discontinuation of study drug, and drug-related TEAE leading to death.

The following summaries will also be provided for the PLS, summarized by the MedDRA preferred term:

- Incidence of drug-related TEAEs by preferred term
- Incidence of serious drug-related TEAEs by preferred term

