(Down-Titration Period). A Down-Titration Visit (DTV) will be performed at the end of the Down-Titration Period, and study drug will be discontinued at the DTV. After 2 weeks free of study drug (Safety Period), study participants will complete the SV.

Brivaracetam (tablet and oral solution) will be administered twice per day in equal doses. The maximum allowed daily dose in EP0132 is 200mg/day (4mg/kg/day). Dose adjustments of BRV and/or concomitant AEDs based on clinical judgment are allowed at any time, 3 days after study start and onwards.

The duration of the study per study participant will be 2 years at minimum, until approval of BRV for the indication of CAE or JAE has been obtained for pediatric participants in their age range, until a managed access program is established as allowed per country-specific requirements in addition to legal and regulatory guidelines, or until the investigational product development in the related indication is stopped by the Sponsor, whichever comes first.

This study will be conducted using a site-based model; all study assessments will be conducted at the study site.

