3.3.3 Three- and six-month periods

A month is defined as 30 days and time intervals based on monthly durations are defined as a multiple of 30 days. The definitions of 3- and 6-month periods are described in [Table 3-3](#) and [Table 3-4](#) respectively.

Table 3-3: Definition of each 3-month period

Period	Days relative to date of first dose in EP0132
Months 1 to 3	1 to 90
Months 4 to 6	91 to 180
Months 7 to 9	181 to 270
Months 10 to 12	271 to 360
Months 13 to 15	361 to 450
Months 16 to 18	451 to 540
Months 19 to 21	541 to 630
Months 22 to 24	631 to 720
Months 25 to 27*	721 to 810
Months 28 to 30*	811 to 900
Months 31 to 33*	901 to 990
Months 34 to 36*	991 to 1080

Table 3-3: Definition of each 3-month period

Period	Days relative to date of first dose in EP0132
...	...

* These 3-month periods are only applicable for a subset of participants who remain in the EP0132 study past Month 24.

Table 3-4: Definition of each 6-month period

Period	Days relative to date of first dose in EP0132
Months 1 to 6	1 to 180
Months 7 to 12	181 to 360
Months 13 to 18	361 to 540
Months 19 to 24	541 to 720
Months 25 to 30*	721 to 900
Months 31 to 36*	901 to 1080
...	...

* These 6-month periods are only applicable for a subset of participants that remain in the EP0132 study past Month 24.

Three-month periods will be utilized for summaries and analyses of efficacy based on seizure data (diary data), AEs, and other safety endpoints. Six-month periods will be utilized for efficacy analyses of seizure data based on EEG, and consecutive and cumulative consecutive absence seizure freedom based on seizure data (EEG and diary data). For the analysis of AEs, participants will be included in 3-month period summaries if the end date of their Evaluation Period is on or after the first day of the 3-month period respectively.

Assessment visits are scheduled based on months calculated as 365.25/12 and thus are not fully aligned to the 3-month or 6-month periods described above. For example, the 7 to 12 month period would end at 360 days whereas the Month 12 visit is scheduled at 365 days. Similarly, the 19 to 24 month period would end at 720 days whereas the Month 24 visit is scheduled at 731 days. Further details are provided in [Table 3-5](#).

Table 3-5: Study periods vs scheduled assessments

Period	Days relative to date of first dose in EP0132	Scheduled assessment visit ^a	Scheduled assessment visit (days)
Months 1 to 3	1 to 90	MEV, Month 3	91

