3.3.10 Calculation of modal dose

Modal dose categories will be calculated across all study days on or after the day of first dose of BRV in EP0132 and up to and including the day of last dose of BRV in the Evaluation Period (excluding the Down-Titration Period). Modal dose is calculated as the most frequently taken daily dose category during this period. Modal dose will be categorized as defined in [Table 3-6](#).

Table 3-6: Dose group definitions for calculation of modal dose

Daily dose category (mg/day) ^a	Equivalent mg/kg/day ^b	Dose group label
>0 to <100	>0.0 to <2.0	>0.0 to <2.0 mg/kg/day
≥100 to < 150	≥2.0 to <3.0	≥2.0 to <3.0 mg/kg/day
≥150 to <200	≥3.0 to <4.0	≥3.0 to <4.0 mg/kg/day
≥200	≥4.0	≥4.0 mg/kg/day

^a Daily dose category is modified for participants weighing less than 50kg.

^b For participants weighing ≥50kg, the dose in mg/kg/day is calculated based on a weight of 50kg. The permitted dose range for all participants is between 1 and 4 mg/kg/day.

To calculate modal dose, the following steps will be applied:

1. The total daily dose in mg/kg/day will be classified into 1 of the above categories on a daily basis
 - All participants are assigned 100 mg/day (or equivalently 2.0 mg/kg/day for study participants weighing less than 50kg) at the EV.
 - At the Telephone Call visit, the dose may be adjusted to 50 to 200mg/day (or equivalently 1.0 to 4.0 mg/kg/day for study participants weighing less than 50kg). This is documented on the Study Drug Dispensation and Administration eCRF. If 'maintain dose' is selected, the dose is continued from the EV. If 'modify dose' is selected then the new dose is documented in mg/day, and will be used to calculate the daily dose in mg/kg/day. It is assumed that any new dose is first taken the morning after it is dispensed.
 - Any subsequent changes to the daily dose in mg/day will be documented on the Study Drug Collection Dispensation and Administration eCRF. If 'maintain dose' is selected, the dose is continued from the 'daily dose at last visit' entered on the eCRF at that visit. If 'modify dose' is selected, then the new dose is documented in mg/day and will be used to calculate the daily dose in mg/kg/day.
 - For participants with body weight <50kg, the total daily dose in mg/kg/day will be the total daily dose in mg divided by the most recently available body weight in kg.
 - For participants with body weight ≥50kg, the total daily dose in mg/kg/day will be the total daily dose in mg divided by 50kg.

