 - Each daily dose will then be classified into 1 of the daily dose categories in mg/kg/day. The total daily dose will be attributed to a specific period (the Evaluation Period and additionally a 3-month period as defined in [Table 3-3](#)).
2. Once all total daily doses are converted to mg/kg/day and classified into 1 of the above categories, the modal dose is the dose category which was most frequent within the specific period. In the event of a tie, the modal dose will be set to the lower of the tied dose categories.

The modal dose category will be calculated for each 3-month period the participant enters regardless of the number of days completed in this period. A participant is considered to enter a

period if the end date of the Evaluation Period is on or after the first day of the relevant 3-month period.

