3.13.13 Dose at AE onset

The dose of study drug the study participant was taking at the onset of an AE will be derived as the most recent daily dose (in mg) reported in the Study Drug Collection Dispensation and Administration eCRF, prior to the onset date of the AE. AEs with onset date on the same day as a dose level change will be considered to have started prior to the dose change and will therefore be attributed to the preceding dose level. For AEs with an onset date on the same date as the EV, the dose at onset will be the prescribed starting dose of 100mg/day (or equivalently 2mg/kg/day for study participants weighing less than 50kg). For participants whose dose has been maintained throughout the study since the EV, the prescribed starting dose will be used as the dose at AE onset throughout the study.

The dose at AE onset will not be derived for AEs ongoing from N01269.

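### The only planned TEAE-by-dose table groups participants by modal dose, so events followed or preceded by a dose change can be credited to a category not taken at onset, in either direction

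*SAP*

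**What the plan says.** SAP 10.2.1 defines an overall TEAE summary: any TEAE, serious, requiring dose change, drug-related, severe, leading to discontinuation, and death. It adds that "this summary will be presented by modal dose category for the Evaluation Period and for each 3-month period in the Evaluation Period". The System Organ Class and Preferred Term tables in the same section are not specified by dose.

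The grouping variable is defined in SAP 3.3.10: "Modal dose is calculated as the most frequently taken daily dose category during this period". There are four categories, with boundaries at 2.0, 3.0 and 4.0 mg/kg/day (Table 3-6). The tie rule is: "In the event of a tie, the modal dose will be set to the lower of the tied dose categories". The category is recomputed by period: "The modal dose category will be calculated for each 3-month period the participant enters regardless of the number of days completed in this period". Down-titration days are left out. SAP 10.1 assigns participant-years the same way, so a participant's full Evaluation Period exposure goes to his or her modal category.

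Dose is flexible within a participant. SAP 3.3.10 fixes the start: "All participants are assigned 100 mg/day (or equivalently 2.0 mg/kg/day for study participants weighing less than 50kg) at the EV". Protocol 4.1 then permits changes: "Dose adjustments of BRV and/or concomitant AEDs based on clinical judgment are allowed at any time, 3 days after study start and onwards".

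Dose at onset "will be derived as the most recent daily dose (in mg) reported in the Study Drug Collection Dispensation and Administration eCRF", taken before the onset date (SAP 3.13.13). SAP 10.2.2 includes it in the AE listings. No table uses it. SAP 3.2 and 3.8 allow selected outputs by modal or maximum dose, but these are optional and neither is tied to onset.

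**The concern.** The grouping is settled after the fact, and the outcome being tabulated can influence it. A TEAE may prompt a dose change, and 10.2.1 itself counts TEAEs with a reduction or an increase as a row of the table. A participant who has an event at a higher dose, is reduced and then continues for long enough is shown as a lower-dose participant with an event. A participant who has an event at the starting dose and is later raised is shown as a higher-dose participant with an event.

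Long-term safety and tolerability is the primary objective, and this is the one TEAE-by-dose display the SAP commits to. Readers will compare its columns even though no test is attached. The risk is that a real dose pattern is flattened or inverted, or that one appears where there is none.

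**Working it through.** The plan gives no figure to reproduce: there is no sample-size calculation and no hypothesis test. The check has two parts.

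**1. Day counts under the SAP rule.** SAP 3.3.3 says "time intervals based on monthly durations are defined as a multiple of 30 days", so 3 months is 90 days and 24 months is 720 days. The safety Evaluation Period is not cut at Month 24, so 720 is used as the 24-month case. Take two dose levels, with H higher-dose days out of L.

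- *Downward.* The higher level is not the mode if H ≤ L − H, that is H ≤ L/2, with the tie counting as lower. The limit is 720/2 = 360 days, or 90/2 = 45 days.
- *With the assigned start.* Assume the starting category on days 1–14, a higher category from day 15, an event on day t, and the starting category again from day t+1. Then H = t − 14, and the event is credited downward if t ≤ 14 + L/2: up to day 59 of 90, or day 374 of 720. Later events stay with the higher category.
- *Example.* For an event on day 44, H = 44 − 14 = 30. Lower-dose days are 14 + (720 − 44) = 690. The event and all 720 days of exposure go to the lower category. In Months 1–3 the count is 30 against 60, so it goes lower there too.
- *Upward.* For an event in the starting category on day t, with a raise from day t+1 that is kept, the lower level has t days and the higher L − t. The event is credited upward if t < L/2: up to day 44 of 90, or day 359 of 720. The event need not cause the raise. For a participant raised on day 15 and kept there, Months 1–3 count 14 lower and 90 − 14 = 76 higher days, so any event on days 1–14 is shown at the higher dose.

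**2. Can this alter the visible pattern?** An illustrative simulation used N = 140 (the expected rollover), 720 days, no dropout and 150 replicates per scenario. These inputs are assumptions that are not in the documents: half of participants raised on day 15; a first-event rate at the lower dose of 0.0005, 0.001 or 0.002 per day; a true rate ratio, higher to lower, of 1.5, 2 or 3; and a probability of 0, 0.5 or 0.8 that a higher-dose event leads to reduction. Results at 0.0005 per day:

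| True ratio | Reduced after event | Evaluation Period by modal dose, lower vs higher | 3-month tables, higher/lower | By dose at onset, rate ratio |
|---|---|---|---|---|
| 1.5 | 0 | 30.1% vs 41.7% | 1.39 | 1.52 |
| 1.5 | 0.5 | 37.2% vs 34.0% | 0.95 | 1.52 |
| 1.5 | 0.8 | 40.9% vs 28.4% | 0.75 | 1.52 |
| 2 | 0 | 30.1% vs 51.0% | 1.69 | 2.00 |
| 2 | 0.5 | 39.1% vs 42.7% | 1.16 | 2.00 |
| 2 | 0.8 | 43.6% vs 35.9% | 0.91 | 2.00 |
| 3 | 0 | 29.8% vs 65.7% | 2.20 | 3.09 |
| 3 | 0.5 | 41.9% vs 56.6% | 1.49 | 3.09 |
| 3 | 0.8 | 47.2% vs 48.7% | 1.23 | 3.09 |

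Over all 27 scenarios, the Evaluation Period table reversed the direction in 7 and the 3-month tables in 4. All of these were among the 18 scenarios with reductions. None of the 9 without reductions reversed. Rates by dose at onset, per person-time to first event, recovered the assumed ratio throughout (for example 18 vs 37 per 100 participant-years at a true ratio of 2).

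Two limits apply. The modal-dose columns are proportions and the onset column is a rate ratio, so they would differ somewhat even without misplacement: 51.0/30.1 = 1.69 with no reductions at a true ratio of 2. And the simulation mainly exercises the downward path. Upward misplacement enters only through events on days 1–14, and escalation after an event is not modelled.

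**The case against.** The strongest reply is that little depends on this table. No objective or estimand concerns a dose relation. The primary measure is TEAE incidence in all treated participants, in a single-arm, individually titrated study with no testing. SAP 3.8 makes syndrome and all participants the standard presentation precisely because doses vary so much. Only the overview table is split by modal dose. The listings show dose at onset and action taken, so any misplaced event can be traced. Recomputing the mode in each 90-day period limits the damage. All of this stands, and it keeps the point modest. It does not make the specified table readable by dose, and listings are a poor substitute for a summary.

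A reader might also infer that every event followed by a reduction is credited to the lower dose, or that the table is biased toward making higher doses look safer. The documents support neither. Downward crediting needs a change that crosses a category boundary and enough lower-dose days in that period. Stopping treatment adds no lower-dose days, because down-titration is excluded. Events before an escalation are misplaced the other way, and every participant begins in the category from 2.0 to below 3.0 mg/kg/day, with room to go up. The net direction depends on escalation and reduction rates that neither document gives.

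Finally, a table by dose at onset would not be causal either. Dose is not randomised, titration follows response and tolerability, and early events cluster at the starting dose. That is correct, and it limits what the remedy can claim.

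**Conclusion.** The concern holds as a possibility of misclassification in both directions, in one descriptive table. With two dose levels, up to 360 of 720 higher-dose days (45 of 90) can be credited to the lower category together with the event. Events up to day 359 of 720 (44 of 90) can be credited upward after a lasting escalation. Under assumed but not extreme inputs, the Evaluation Period table can shrink, hide or reverse a true dose relation. The 3-month tables are generally affected less, but they are not free of it.

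The day-count limits follow from the SAP rules alone. The simulated percentages rest on assumed event rates, escalation share and reduction probabilities, so they show what can happen, not what to expect here. No primary or secondary result changes. Because the remedy is cheap and the table is the only committed view of TEAEs by dose, it is worth making the change.

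**What to change.** Keep the modal-dose table in SAP 10.2.1, with a footnote that participants are classified on all days of the period, including those after an event, and that the table does not support inference about a dose relation.

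Add the same overall TEAE summary by dose category at onset. Convert the 3.13.13 dose to mg/kg/day with the 3.3.10 weight rules, and use participant-years actually spent in each daily dose category as the denominator. A participant may then contribute to more than one column. State whether person-time in a row stops at the first event, as it does in the calculation above.

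The cost is a short SAP edit and modest programming. The onset dose and the daily dose categories are already derived, but 3.13.13 is in mg/day and SAP 10.1 plans participant-years only by modal category, so the conversion and the time-varying exposure are new. The added table should carry its own note that it is descriptive and remains confounded by non-randomised titration and by time on drug.

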10.2.2 AE listings

All AEs reported during the study will be provided in study participant data listings for the ASPS Set.

AE listings will include AE onset date, AE outcome date, AE duration (defined in [Section 10.2](#)), dose level at onset (defined in [Section 3.13.13](#)), whether the AE was serious, AE intensity, whether the AE was treatment-emergent, whether the AE was related to COVID-19 vaccination, the pattern of the event, whether the event was ongoing from N01269, whether the AE lead to dropout, whether the AE was of special interest, whether the AE was of interest, relationship to study medication, action taken with study medication, other action taken, and AE outcome.

The following AE listings will be provided:

- Glossary for all AEs
- All AEs
- All serious AEs
- All AEs leading to study discontinuation
- All deaths
- COVID-19 vaccination related AEs

Should they occur, any uncoded AEs should be designated as “coding-pending” at all MedDRA levels, and such AEs should be included in summary tables and study participant data listings based on this classification (eg, SOC and PT set to coding-pending).

10.3 Clinical laboratory evaluations

10.3.1 Hematology, Clinical chemistry, Endocrinology and Urinalysis parameters

Hematology, clinical chemistry, and urinalysis variables are assessed at MEV, FEV, YEV, FV, and EDV, and will also be assessed at SV if abnormal at the FV or EDV. For study participants on study drug for more than 12 months, laboratory assessments at MEV can be omitted.

Endocrinology variables are assessed at the YEV/FV for study participants aged <18 years.

Observed results as well as CFB will be summarized descriptively, by visit, for all laboratory variables.

The definition of PCS is described in [Section 3.4](#). The criteria for a laboratory value to be PCS are defined in [Section 13.1.1](#) and [Section 13.1.2](#). All laboratory measurements will be assessed to determine if they meet PCS criteria. The number and percentage of study participants with PCST values for each laboratory variable (ie, PCST low value, PCST high value) for hematology, biochemistry, endocrinology and urinalysis will be summarized, over all visits (including unscheduled visits) and by visit separately. Percentages in the overall summary will be relative to the number of study participants with at least one assessment on or after the first dose of BRV in EP0132. Percentages in the by visit summary will be relative to the number of study participants with a measurement at the visit. Note that the urinalysis variables nitrites, pH, and specific gravity will not be assessed against PCS criteria and thus will be listed only.

For female participants of childbearing potential, a urine pregnancy test is performed at MEV, FEV, YEV, FV or EDV as applicable, and SV. A urine pregnancy test may also be performed at unscheduled visits. Serum pregnancy tests are performed for PDILI assessments and local laboratory assessments. Pregnancy test results will not be summarized.

Summaries of laboratory variables will only summarize variables planned per the protocol, however, both planned and unplanned laboratory variables will be provided in data listings. Unscheduled laboratory tests conducted by local laboratories are unplanned so will be included in the listings only.

Summaries and listings of study participants with PCST values for laboratory variables will include all planned and unplanned variables from central and local laboratories. In the unlikely event that there are both central and local laboratory measurements on the same calendar date, preference will be given to the central laboratory result. Summaries of PCST values for urinalysis will only include data from central laboratories.

A listing of additional laboratory tests will be provided including urine and serum pregnancy tests and urine drug screen tests (performed as part of the PDILI assessments described in [Section 10.3.2](#)).

